8. STUDY PROCEDURES

- Refer also to [Schedule of Assessments](#)

8.1 Screening and Enrollment Steps

Week 0/Screening and Baseline Assessment

Participants will be screened, consented, and enrolled entirely online using electronic data capture. Parents/Guardians and coordinators will complete the following steps prior to enrollment via online forms:

- Screening questionnaire completed online
- Informed Consent administered and obtained online (waiver of documentation approved)
- Baseline questionnaires completed (Demographics, Mobile Autism Risk Assessment (MARA), Parent Stress Scale, VABS-3 Socialization subscale parent report, Emotion Recognition Child online Task
- review of baseline data completed by coordinator

Week 1: Enrollment and Allocation

- Upon receiving notification with download link and download access code, participant downloads the app and is automatically randomized to treatment or control using a pre-defined block randomization scheme developed by the statistician.

[Weeks 1-4: Intervention](#)

If randomized to Control, participants will continue treatment as usual. When they log-in to the app, they will receive a message that they will wait a few more weeks before beginning treatment.

If randomized to Treatment, participants will be asked to play the app 3 times a week for 10-15 minutes for the next 4 weeks and they will receive weekly push notifications and email reminders.

[Week 4 Post-Test 1](#)

Treatment and Control will be asked to complete all outcome measures and will be asked about any changes in treatment or safety events at week 4. Participants will also be asked to complete a question assessing time spent playing with their child over the last month in emotion-centric theatrical play.

[Week 8 Post-test 2](#)

At week 4 from initial app download date, participants will be asked via email to complete all outcome measures as well as check-in on any changes in treatment and any safety events. These will be collected via RedCap online surveys.

[Week 12 Post-test 3 Follow-Up](#)

Treatment and Control will be asked to complete all outcome measures and will be asked about any changes in treatment or safety events at week 4. Participants will also be asked to complete a question assessing time spent playing with their child over the last month in emotion-centric theatrical play.

9. EFFICACY AND SAFETY ASSESSMENTS

9.1 Efficacy Assessments

[Primary Measurement \(Efficacy\):](#)

1. Change in Vineland Adaptive Behavior Socialization Parent Report from baseline (week 0) to week 4

Vineland Adaptive Behavior Scales, 3rd edition (VABS-3) Socialization subscale of the Parent/Caregiver Comprehensive form will be administered online to the parents. Scores from the socialization domain of the VABS-3 reflects one's functioning in social situations. The socialization subscale is up to 112 items depending on age and development, where raw scores are converted to IQ-type standard scores--v-scale scores ($M=15$, $SD=3$) where scores range from 1 to 24, and factor in age equivalents, growth scale values, and higher scores indicate better adaptive functioning

[Secondary Measurements \(Efficacy\):](#)

1. Change in Parent Stress Scale from baseline (week 0) to week 4

The Parental Stress Scale is an 18-item parent report scale that evaluates the extent of parent stress. Scores range from 18-90, where higher scores indicate a higher level of Parental stress.

2. Change in Child Emotion Recognition score from baseline (week 0) to week 4

Study team will use an image-based emotion recognition task where participants will select the emotion that corresponds to an emotional facial image in the form of a GIF (Graphics Interchange Format) image. Participants will select 1 of 8 available Ekman emotion labels for 16 facial emotional image stimuli presented in random order.

Correct responses will be measured against a predetermined majority rules consensus of the emotional content of the GIFs.

3. Change in Vineland Adaptive Behavior Socialization Parent Report from baseline (week 0) to week 4
4. Change in Parent Stress Scale from baseline (week 0) to week 4
5. Change in Child Emotion Recognition score from baseline (week 0) to week 4

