5.2 Secondary Objectives

To see if use of a social game-based digital therapeutic can lead to changes in emotion recognition and parent stress when used consistently over 4 weeks.

To understand whether there is a difference in clinically meaningful changes if the device is used 4 weeks continuously.

To understand what demographic variables (if any) make patients more likely to respond to the treatment.

To understand the safety of device when used at home with a parent/caregiver.

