7. STUDY TREATMENT - GUESSWHAT

7.1 Study Intervention

We invented a digital treatment, GuessWhat, that operates on smartphones to create a fluid social engagement with an autistic child and his/her social partner to reinforce prosocial learning while simultaneously collecting game metric and video data that can be used to measure the child's progress and symptoms. The GuessWhat app challenges the child to interpret and imitate social and emotion-centric prompts shown on the screen of a smartphone held just above the eyes of a parent/guardian. The parent flips the phone upward/downward if able/unable to correctly guess what the child is acting, switching to the next image in the deck with each flip. The phone's front camera (facing the child) records the entire gameplay session and after each gameplay session, caregivers can choose to share the video with our research team.

Preliminary work to-date resulted in positive user feedback, evidence of engagement for both the parents and children, and meaningful gains in socialization in the child.

Parents and children choose from a variety of different game decks, with decks showing faces emoting the standard Ekman emotion expressions, cartoon characters playing sports activities, occupations, etc. Key mechanisms include facial expression labeling, imitation of varied social emotional prompts, and joint attention with a social partner during play to act out prompts and earn points.

[figure not shown]

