Figure 1. Mobile Intervention User Experience. GuessWhat is a mobile game available for any smartphone device that uses varied a) reward systems, and b) social emotional games to help children practice facial expression and emotion recognition, joint attention, and play. In a typical game session, c) the parent and child play a round of “MojiMatch” where the child matches an emoji to an animated GIF of a facial expression. Afterwards, the parent reviews and makes their own choices about the expression. d) Then they play “Act it Out,” where the parent holds the smartphone to their forehead and tries to guess the emotion mimicked by the child in response to the prompt shown on the phone’s screen. Upon guessing, the parent tilts the phone to proceed to the next prompt through the end of the session. After each game, parent and child can review a video of the session together. In-app game modes, unlocking deck and character choices based on coins earned, and activity-based achievement badges reinforce positive progression and ensure optimal child engagement through time.

Standard Dose

GuessWhat is a digital therapeutic application intended to improve socialization skills including joint attention and facial expression/emotion recognition in children with Autism Spectrum Disorder (ASD) between the ages of 3 and 12 years old. It is designed to be used regularly with a **caregiver 3-4 times a week for 15-20 minutes**. GuessWhat is intended for use as a part of a therapeutic program that may include clinician directed therapy, medication, and/or education programs, which further address symptoms of ASD.

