10.5 Stratification, Subgroup Analysis and Pooled Analysis

Following consent, those subjects meeting all entry criteria will be randomized in a 1:1 ratio. Random blocks of size 2 or 4 will be utilized.

[Efficacy Endpoint Analysis](#)

1. Objective

To compare the change in outcome measure scores between treatment and treatment as usual groups in a clinical trial.

2. Study Design

Participants: Treatment and Treatment as Usual groups

Outcome Measure: Continuous outcome measure scores measured at baseline and follow-up on VABS-3 Socialization Subscale and Parent Stress Scale.

3. Statistical Hypotheses

Null Hypothesis (H_0): There is no difference in the change in outcome measure scores between treatment and control groups.

Alternative Hypothesis (H_1): There is a significant difference in the change in outcome measure scores between treatment and control groups, whereby treatment participants scores demonstrate improvement.

4. Variables

Independent Variable: Group (Treatment vs. Control)

Dependent Variable: Change in outcome measure scores (Post-test score - Pre-test score)

5. Statistical Method

Primary Analysis: Independent samples t-tests will be used to compare the mean change in outcome measure scores between treatment and control groups.

6. Assumptions

Normality: The change in outcome measure scores in each group should be approximately normally distributed. If not, consider transformations or non-parametric tests.

Equal Variances: The variances of change scores in the treatment and control groups should be approximately equal. If violated (checked using Levene's test), use Welch's t-test or report results with caution.

7. Statistical Software

Analysis Tool: SPSS, R, or any other statistical software capable of performing independent samples t-tests.

Descriptive analyses

Descriptive statistics (proportions for categorical variables, means, medians, standard deviations, and interquartile ranges for continuous variables) will be reported for all key patient variables, including baseline and demographic characteristics, use of medications, compliance, and study completion status. Data that are missing on key patient characteristics and the outcome will be fully described, including any patterns of missingness (i.e., any relationships between missingness of a variable and patient characteristics).

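### The emotion-recognition test closely resembles a game only the treatment arm plays, its GIFs are not kept out of the app, and the outcome list in 10.5 omits this endpoint

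*Combined protocol and SAP*

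**What the plan says.** The synopsis and section 9.1 make the week 0 to week 4 change in Child Emotion Recognition score a secondary efficacy endpoint. Section 5.2 asks whether the app "can lead to changes in emotion recognition and parent stress when used consistently over 4 weeks".

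**The test.** Section 9.1 has participants "select the emotion that corresponds to an emotional facial image in the form of a GIF (Graphics Interchange Format) image". It continues: "Participants will select 1 of 8 available Ekman emotion labels for 16 facial emotional image stimuli presented in random order". The key is described as follows: "Correct responses will be measured against a predetermined majority rules consensus of the emotional content of the GIFs". The source of the GIFs is not given.

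**The app.** In MojiMatch, part of a typical session, play is described as one "where the child matches an emoji to an animated GIF of a facial expression" (section 7.1, Figure 1). The parent then reviews and makes a separate choice. Section 7.1 also describes "decks showing faces emoting the standard Ekman emotion expressions" and states: "Key mechanisms include facial expression labeling, imitation of varied social emotional prompts, and joint attention with a social partner".

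**Who plays.** Under section 8.1, weeks 1-4, controls who log in are told to wait. Section 7.2 describes the download link as going to treatment participants. On either description, controls have no game play before week 4.

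**The analysis.** The outcome measure entry in section 10.5 reads: "Continuous outcome measure scores measured at baseline and follow-up on VABS-3 Socialization Subscale and Parent Stress Scale". Emotion recognition is not in it.

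**The concern.** Two separate things are at issue.

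The first is interpretation. Repeating the same test at week 4 gives both arms the same retest practice, so that cancels in the between-arm difference. Practice from the app does not cancel, because only one arm has it. Randomization cannot remove an exposure that is part of the treatment. Some of that practice is the intended effect: the app is meant to improve recognition of expressions. Recall of particular clips is not. If a test GIF also appears in MojiMatch, a correct answer at week 4 may mean only that the child has seen that clip before.

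This matters more than usual for a secondary endpoint. The other two efficacy measures in 9.1 are parent reports, and section 4.1 says outcome assessors are not blinded. The plan does not assign the child task a corroborating role, but readers are likely to give it one.

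The second is prespecification. An endpoint that the synopsis and 9.1 call efficacy, but that the list in 10.5 leaves out, can later be reported or dropped without departing clearly from the plan.

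**Working it through.** **1. Test and game side by side**

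| | Endpoint (9.1) | MojiMatch (7.1, Figure 1) |
|---|---|---|
| Stimulus | Facial-expression GIF | Animated facial-expression GIF |
| Response | 1 of 8 Ekman labels | Emoji |
| Emotion set | Ekman | App decks include Ekman expressions |
| Exposure before week 4 | Both arms | Treatment arm only |

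The tasks are close but not identical; the response symbol differs. No section says where the 16 GIFs come from or that they are absent from the app.

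**2. The plan's own figure**

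Section 10.2 gives 180 completers per arm for 90% power at two-sided 0.05 to detect 3.1 points on VABS-3 Socialization. It states no SD. Solving back:

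SD = 3.1 × √(180/2) / (1.960 + 1.282) = 9.07.

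This concerns the primary endpoint only. No effect size or SD is given for emotion recognition.

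**3. How small a familiarity effect would show (illustration)**

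- From the plan: 180 per arm, two-sided 0.05, 16 items, 8 options (pure guessing scores 16/8 = 2).
- Assumed: SD of change of 2, 3 or 4 items.
- SE of the difference = SD × √(2/180) = 0.1054 × SD.
- Difference detectable at 90% power = (1.960 + 1.282) × SE = 0.342 × SD.
- Probability of significance for a gain g ≈ Φ(g/SE − 1.960).

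| Assumed SD (items) | SE | Detectable at 90% power | g = 1 item | g = 0.5 item |
|---|---|---|---|---|
| 2 | 0.211 | 0.68 | 99.7% | 66% |
| 3 | 0.316 | 1.03 | 88.5% | 35% |
| 4 | 0.422 | 1.37 | 66% | 22% |

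**4. How many shared GIFs would give 1 item (illustration)**

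Let k be the number of shared GIFs, p the rise in the chance of a correct answer on a shared GIF, and u the share of treated children who meet it. The mean gain is k × p × u, so k = 1/(p × u) gives 1 item. The values of p and u are assumptions.

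- u = 1, p = 0.40 to 0.20: k = 2.5 to 5.
- u = 0.5, p = 0.40 to 0.20: k = 5 to 10.

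Exposure may well be low. Feasibility families averaged 18 sessions of 90 seconds (section 3.2), that is 18 × 1.5 = 27 minutes, over six days of use. The gain also cannot exceed 16 minus the baseline score.

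**5. Can the comparison be made as the plan stands?**

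The section 13 schedule has the child task at weeks 0 and 4. Section 8.1 has both arms complete all outcome measures at week 4. The t-test wording in the synopsis and 10.5 is generic, and section 10.4 puts all efficacy analyses in the ITT population. So a between-arm change can be estimated. The gap is that 10.5 does not name this endpoint where it names the others.

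**The case against.** The strongest reply is that closeness to training is partly the point. Labelling facial expressions is a named mechanism, and an outcome proximal to the mechanism is a legitimate secondary endpoint. That stands. The concern is limited to memory of particular clips and does not make the endpoint invalid.

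It is also fair to say that item overlap is argued from silence. A reader might infer that the test GIFs come from the app library because the same group runs the study. The documents do not say so. Nor do they show that the child learns an answer from the parent: Figure 1 has the parent making a separate choice, and section 9.2 tracks parent-child disagreement. The test is scored against a consensus key.

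The sizes in the working rest on assumed SDs, gains and exposure. Low app use, a choice among games and decks, and non-users kept in the ITT population would all dilute any effect. This also stands, and is why the figures show sensitivity and are not an estimate of bias.

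On 10.5, the generic wording can be read to cover every efficacy endpoint. That limits the consequence, but does not remove the conflict between an explicit two-item list and the endpoints in the synopsis and 9.1.

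**Conclusion.** The point holds in a limited form. The endpoint closely resembles a game that only the treatment arm plays before week 4, and the plan contains no safeguard against shared GIFs. If some are shared, a positive result could not be separated from familiarity with those clips. Whether any are shared, and how large the effect would be, cannot be derived from the documents. The illustration shows only that about one item in 16 could be enough, under an assumed SD of change of 2 to 4 items and 180 completers per arm.

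The omission from 10.5 is a separate internal contradiction. A reader might conclude from the two together that the secondary objective cannot be answered. The documents do not support that: both arms are scored at weeks 0 and 4, the stated t-test can be applied, and the same objective covers parent stress, which 10.5 does list.

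This is an inexpensive improvement to a secondary endpoint. It does not affect the primary analysis.

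**What to change.** **Section 9.1.** State the source of the 16 test GIFs and require that none appears in any GuessWhat deck before the week-4 assessment. If the task is already in use and a check finds shared items, score the endpoint, or a prespecified sensitivity analysis, on the items not in the app. Fix the list of those items before scores are compared by arm.

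**Section 10.5.** Add the week 0 to week 4 change in Child Emotion Recognition score to the outcome measures, as a secondary between-arm comparison in the ITT population.

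**Cost.** A check of 16 GIFs against the app library, and one added line. If shared items are dropped, the score rests on fewer items and loses precision. If GIFs are instead taken out of the app mid-study, the intervention changes for later participants, so rescoring is the simpler route once the task is in use. The observed gain may be smaller. Held-out items remove memory of clips but not practice with the format, so a gain would still need to be described as improvement on a task similar to the one trained.

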9.2 Descriptive/Exploratory Measurements

1. Game metric Analysis for Treatment participants
 - Average duration (average time playing per day)
 - Average frequency (days played per week) of play
 - % Moji Match GIFs with disagreement between parent and child
 - Average emotion confusion for each of the Ekman emotions pre vs. post
 - Average time to guess in Act in Out
 - Time spent acting out a prompt, by prompt type (Sports, Emotions, Occupations, etc.)
 - Frequency of correct vs. incorrect guesses during Act it Out
2. treatment regimen compliance
3. demographics
4. missing data

9.3 Safety Assessments

Adverse Events

Definition of an Adverse Event

The FDA Safety Guidance, referencing 21CFR312.32(a), defines an Adverse Event as follows:

Adverse event means any untoward medical occurrence associated with the use of a drug in humans, whether or not considered drug related.

An adverse event (also referred to as an adverse experience) can be any unfavorable and unintended sign (e.g., an abnormal laboratory finding), symptom, or disease temporally associated with the use of a drug and does not imply any judgment about causality. An adverse event can arise with any use of the drug (e.g., off-label use, use in combination with another drug) and with any route of administration, formulation, or dose, including an overdose.

Evaluating and Reporting of Adverse Events

All AEs will be promptly documented on the Adverse Event in RedCap and assessed by the Principal Investigator. Details of the event must include the dates of onset and resolution, severity, relationship to study drug, seriousness, and whether the event caused the subject to withdraw from the study, outcome and timing with regard to administration of the study drug.

Severity: Severity should be graded and recorded as follows:

- Mild: Awareness of event but easily tolerated
- Moderate: Discomfort enough to cause interference with usual activity

- **Severe:** Inability to carry out usual activity, incapacitating, requires medical intervention

Relationship: The relationship of the Adverse Event to the study device will be determined initially by the Investigator, and assessed using the following definitions:

- **Related:** There is a distinct temporal relationship between the event onset and administration of the study drug. There is a known reaction to agent or chemical group or predicted by known pharmacology. The event cannot be explained by subject's clinical state or other factors.
- **Unrelated:** Evidence exists that the AE has an etiology other than the study drug (e.g., pre-existing condition, underlying disease, intercurrent illness, or concomitant medication).

Final determination of relatedness will be made by the Stanford Institutional Review Board during an unanticipated problem or adverse event submission.

Expectedness: Whether or not the event was expected or unexpected. Further details on this can be found in section 8.5.

These criteria, in addition to good clinical judgment, should be used as a guide for determining the causal assessment. If it is felt that the event is not related to study therapy, then an alternative explanation should be provided.

Serious Adverse Events (SAEs)

Suspected Unexpected Serious Adverse Reactions (SUSARs)

A SUSAR carries specific and time-based reporting requirements for the Sponsor of a clinical trial. Thus, after a Site Investigator reports an SAE, the FDA expects the Sponsor will determine whether it meets the definition of a SUSAR.

A SUSAR is defined according to 3 criteria:

1. The AE is deemed a “suspected adverse reaction” if there is a reasonable possibility that the study drug caused the AE. A “reasonable possibility” means there is evidence to suggest a causal relationship between the drug and adverse event.
2. The AE is “Serious” if it meets the definition of an SAE.
3. The AE is deemed “unexpected” if it is not listed in the Investigator’s Brochure (IB) or if in the IB, has not been reported at the severity observed.

In cases where the Investigator deems a SUSAR has occurred, it must file an IND Safety Report with the FDA. FPHU will require the assistance and cooperation of the Investigator and staff to provide accurate and complete information on the subject and observed SAE so that reporting requirements to the FDA can be met.

Reporting SUSARs to the FDA: IND Safety Reports

IND safety reports are used to submit reports of SUSARs to the FDA. There are 2 types of reports:

- A “15-day report” is used when the reported SAE is a SUSAR and requires that as much information as is available to the investigator and the sponsor, be submitted to the FDA in on the appropriate form. For US trials, the appropriate form is the FDA Form 3500A also commonly known as a “MedWatch” form.
- A “7-day report” is used when the SUSAR is considered to be fatal or life-threatening.

The 7-day and 15-day timelines begin the day that the Sponsor determines the information qualifies for reporting and are counted in calendar days – not business days. Therefore, it is important that the Site investigator carefully follow the reporting requirements.

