A CONSORT diagram displaying the number of patients screened, eligible, and consented along with reasons for ineligibility will be provided. Graphical tools such as histograms, boxplots, and scatterplots will be created to assess quality of data and to display patterns over time.

Safety Analysis

Treatment related adverse events for GuessWhat intervention will be presented. Any adverse events occurring during any phase of the study judged by clinical sites' Primary Investigator (PI) to be related to the intervention will be recorded and presented in a table listing. The Safety population (see [analysis population details](#)) will be used for this analysis that will include randomized participants. The severity of each event will be evaluated by the PI and presented with the recorded events. If there are frequently occurring treatment related adverse events,

a frequency table will be included, to rank events from most frequent to most rare. Subjects will be included in the actual treatment group received.

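### The definition of a Related adverse event is drug wording that does not fit a phone app and leaves some events in neither class, so app-related events may be under-classified

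*Combined protocol and SAP*

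**What the plan says.** Section 7.1 describes the intervention: "We invented a digital treatment, GuessWhat, that operates on smartphones".

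Section 9.3 first frames causality for a device: "The relationship of the Adverse Event to the study device will be determined initially by the Investigator". The definitions that follow are written for a drug.

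- **Related** has three consecutive statements. The first is "There is a distinct temporal relationship between the event onset and administration of the study drug". The second is "There is a known reaction to agent or chemical group or predicted by known pharmacology". The third is that neither the child's clinical state nor anything else accounts for the event. No connecting word says whether one, some or all of these are needed.
- **Unrelated**, the only other class, applies when "Evidence exists that the AE has an etiology other than the study drug".

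Three further statements in 9.3 bear on how these definitions are used.

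- The criteria are guidance to be combined with clinical judgement, and an assessor who considers an event not related should supply another explanation.
- For expedited reporting, an event is a suspected adverse reaction "if there is a reasonable possibility that the study drug caused the AE".
- The investigator's rating is only the initial one: "Final determination of relatedness will be made by the Stanford Institutional Review Board during an unanticipated problem or adverse event submission".

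Section 10.5, under Safety Analysis, says that adverse events which the PI judges "to be related to the intervention will be recorded and presented in a table listing". A frequency table is added if related events are frequent. The synopsis likewise names treatment-related events among its exploratory and descriptive endpoints.

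**The concern.** The causality criteria do not match what is being tested. A game played with a parent could plausibly provoke distress, frustration or dysregulation. Whether such an event counts as Related should depend on timing, on what the game asks of the child, and on whether something else explains it. The written definition instead asks about chemistry and pharmacology.

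The related/unrelated call is also the filter for everything the plan analyses on safety. Section 5.2 makes the safety of home use a secondary objective. The only safety analysis described in 10.5 is a listing, with a possible frequency table, of events judged related. If the definition steers assessors away from Related, or leaves each assessor to decide how much of it to ignore, the listing may understate app-related events or depend on who did the rating.

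**Working it through.** No arithmetic applies. The plan gives no expected adverse event rate, and no figure in it depends on this definition. The check sets the provisions side by side.

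**Step 1: can an app meet the second statement?** Section 7.1 describes software with no chemical agent, so the chemical-group and pharmacology limbs cannot apply. The word for an agent could be stretched to mean the app. A known reaction would then be needed, and section 7.2 (Treatment Precautions) reports no adverse events in testing so far. At the start of the trial, the second statement cannot sensibly be met on any of its limbs.

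**Step 2: classify a test event.** Take a child who becomes distressed during play, with onset clearly linked to the session and no evidence of another cause.

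| Reading of section 9.3 | Related? | Unrelated? | Result |
|---|---|---|---|
| All three statements required | No, the second fails | No, there is no evidence of another cause | Neither class |
| Any one statement suffices | Yes, by timing alone | No | Related |
| Guidance applied with judgement | Open to the assessor | Needs another explanation | Probably Related, but depends on the assessor |

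**Step 3: test the second reading further.** If timing alone suffices, an event that follows play but has a proven other cause is Related by the first statement and also Unrelated. The two classes then overlap. So one reading leaves a gap, another an overlap, and the text does not choose between them.

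**Step 4: the third statement.** Every enrolled child has autism (section 6.1), and the examples given for Unrelated include conditions the child already had. Distress in play can readily be put down to the child's clinical state. If that is suspected but not evidenced, the event fails the third statement of Related and still does not meet Unrelated. This also tends to keep events out of the Related class.

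**Step 5: compare with the other standards.** The expedited-reporting text in 9.3 uses a reasonable possibility of causation, which the test event could satisfy. The same event could therefore be a suspected reaction under one part of 9.3 and not Related under another. In addition, 9.3 gives the IRB the final word on submitted events, while 10.5 tabulates the PI's judgement. The documents do not say which events are submitted or what is tabulated when the two differ.

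**The case against.** The strongest reply is that the definitions are not a mandatory test. Section 9.3 calls them guidance alongside clinical judgement and asks for another explanation when an event is thought not related. For the test event the assessor has none to give, which pushes the call towards Related. Section 10.5 does not repeat the pharmacology clause and refers only to the PI's judgement. This stands, and it rules out a reading that a reader might infer: that no event could ever be classed as Related, so that the listing must come out empty. The documents do not require all three statements, and they let the investigator depart from them.

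It can also be said that nothing is lost. Section 9.3 has all adverse events documented in REDCap with onset, severity, seriousness and relationship, and section 8.1 asks both arms about safety events at week 4. That also stands: a misclassified event could be found and rated again. But re-rating after the data are seen would be post hoc, and 10.5 plans no output for events not judged related.

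A third reply is that a separate threshold for expedited reporting of serious, unexpected events is not in itself an error. This is fair. The comparison matters mainly because that threshold already supplies a workable standard that fits a device. Similarly, asking whether something else explains an event is not peculiar to drugs and may remain as a consideration.

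What none of these replies repairs is that the guidance contains no criterion written for a device. Judgement is being asked to correct the definition rather than to apply it.

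**Conclusion.** The definition is wrong as written. It includes a criterion that this intervention cannot sensibly meet, does not say how its three statements combine, and with Unrelated leaves events that have a time link and no other proven cause in neither class. The likely effect is under-classification or inconsistent classification of app-related events, in a safety analysis limited to events judged related.

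The size cannot be stated. The documents give no event rate, and the effect depends on how far each assessor departs from the written text. The conclusion rests on two assumptions: that assessors give the written definitions some weight, and that section 10.5 is the whole of the planned safety analysis.

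The severity is moderate. The judgement clause and full recording of adverse events limit the harm, the synopsis treats related events as descriptive, and no test or decision rule uses the count. The wording should still be corrected before events are classified.

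**What to change.** In section 9.3:

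- Delete the clause on chemical group and pharmacology, and replace the references to a study drug in the causality text with the app.
- Restate the classes so that they are exhaustive. For example: Related means a reasonable possibility, given timing and the circumstances of play, that use of the app (game demands, screen or camera use, recording or sharing of the session) caused or contributed to the event. Not related means every other event.
- Define reasonable possibility once, in device terms, and use it for both the adverse event rating and the suspected-reaction text.
- Keep the request for another explanation when an event is rated not related.

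In section 10.5, reconcile with 9.3: state whether the PI's or the IRB's determination is tabulated, and list any event on which they differ.

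The cost is a wording change in two sections and one eCRF field. The small downside is that the number of related events may rise.
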